**Table 6-5 Dose reduce criteria of eltrombopag after Week 26**

Dose before decrease	50% decreased dose
150 mg/day	75 mg/day
125 mg/day	75 mg/day or 50 mg/day*
100 mg/day	50 mg/day
75 mg/day	50 mg/day or 25 mg/day*
50 mg/day	25 mg/day
25 mg/day	25 mg Qod

\*When eltrombopag dose need to be reduced by 50% from 125 mg/day or 75 mg/day, the investigators will need to select an appropriate dose level (choose either 75 mg or 50 mg daily for subjects treated with eltrombopag 125 mg/day, and 50 mg or 25 mg daily for subjects treated with eltrombopag 75 mg/day) according to subjects' clinical status.

If subject fails to respond after 26 weeks of treatment, he/she will go off study per [Section 3](#) and [Section 9.1.1](#).

For subjects who do not tolerate the protocol-specified dosing schedule, dose interruptions and/or reductions are either recommended or mandated in order to allow subjects to continue the study treatment.

These dose modifications are summarized in [Section 6.5.1.1](#) and [Section 6.5.1.2](#). Permanent treatment discontinuation is mandatory for specific events indicated as such in [Section 9.1.1](#) and [Section 6.2.2](#).

These dose changes must be recorded on the Dosage Administration Record (DAR) – electronic case report form (eCRF).

#### 6.5.1.1 Dose adjustments for QTcF prolongation

**In case of QTcF  $> 500 \text{ msec}$ , (or QTcF prolongation  $> 60 \text{ msec}$  from baseline)**

1. Assess the quality of the ECG recording and the QT value and repeat if needed
2. Interrupt study treatment
3. Determine the serum electrolyte levels (in particular hypokalemia, hypomagnesemia). If abnormal, correct abnormalities before resuming study drug treatment.
4. Review concomitant medication associated with QT prolongation, including drugs with a “Known”, “Possible”, or “Conditional risk of Torsades de Pointes” (refer to [qtdrugs.org](http://qtdrugs.org)), and drugs with the potential to increase the risk of study drug exposure related QT prolongation
5. Check study drug dosing schedule and treatment compliance
6. Consider collecting a ECG time-matched PK sample as unscheduled PK sample, and record time and date of last study drug intake.

**After confirming ECG reading at site, if QTcF > 500 msec**

- Interrupt study treatment
- Repeat ECG and confirm ECG diagnosis by a cardiologist or central ECG lab
- If QTcF confirmed > 500 msec:
  - Correct electrolytes, eliminate culprit concomitant treatments, and identify and address clinical conditions that could potentially prolong the QT as per the ECG and QTc Clinical Safety Standards Guidelines Section 3.3.1.
  - Consult with a cardiologist (or qualified specialist)
  - Increase cardiac monitoring as indicated, until the QTcF returns to  $\leq 480$  msec.
- After resolution to  $\leq 480$  msec, consider re-introducing treatment at reduced dose, and increase ECG monitoring for the next treatment(s):
  - If QTcF remains  $\leq 500$  msec after dose reduction, continue planned ECG monitoring during subsequent treatment
  - If QTcF recurs  $> 500$  msec after dose reduction, discontinue subject from trial.

**6.5.1.2 Dose interruption due to liver signals**

Eltrombopag dose may be interrupted when clinically indicated at the discretion of the investigator. Recommended dose modifications for isolated ALT or AST elevation are listed in [Table 6-6](#).

**Table 6-6 Criteria for dose reduction / interruption and re-initiation of eltrombopag treatment for adverse drug reactions**

Dose modifications for ETB115	
Investigations (Hepatic)	
Isolated ALT elevation	
> ULN - 3.0 x ULN	Maintain dose level
$\geq 3.0 - 5.0 \times ULN$	Maintain dose level. Repeat LFTs a as soon as possible, preferably within 48-72 hours from awareness of the abnormal results. If abnormal lab values are confirmed upon the repeat test, then monitor LFTs a weekly, or more frequently if clinically indicated, until resolved to $\leq 3.0 \times ULN$ .

Dose modifications for ETB115	
	
Discontinue subject from the study treatment if elevation ALT <math>\geq 3.0 \times</math> ULN in patients with normal liver function, or <math>\geq 3.0 \times</math> baseline or <math>> 5.0 \times</math> ULN, (whichever is the lower, in patients with pre-treatment elevations in transaminases) and are combined with any of the following:
 

• Clinical symptoms of liver injury or evidence for hepatic decompensation

• Progressively increasing LFTsa upon repeat testing

• Persistence for <math>\geq 4</math> weeks

Combined elevations of ALT and total bilirubin	
For subjects with normal liver function at baseline, [ALT $\geq 3.0 \times$ ULN] combined with increased direct bilirubin OR For subjects with elevated baseline ALT [ALT $\geq 3.0 \times$ baseline] OR [ALT $> 5.0 \times$ ULN], whichever is lower, combined with increased direct bilirubin.	Permanently discontinue subject from study drug treatment. Repeat as soon as possible, preferably within 48 hours from awareness of the abnormal results, then with weekly monitoring of LFTs a ), or more frequently if clinically indicated, until AST, ALT, or bilirubin have resolved to baseline or stabilization over 4 weeks.

All dose modifications should be based on the worst preceding toxicity. a Core LFTs consist of ALT, AST, GGT, total bilirubin (fractionated [direct and indirect], if total bilirubin  $> 2.0 \times$  ULN), and alkaline phosphatase (fractionated [quantification of isoforms], if alkaline phosphatase  $> 2.0 \times$  ULN.)

In this study, one dose level is equal to 25 mg eltrombopag. Eltrombopag can cause hepatobiliary laboratory abnormalities, severe hepatotoxicity, and potentially fatal liver injury. Serum ALT, AST and bilirubin should be measured prior to initiation of eltrombopag, every 2 weeks during the dose adjustment phase and monthly after establishment of a stable dose. Abnormal serum liver tests should be evaluated with repeat testing within 3 to 5 days. If the abnormalities are confirmed, serum liver tests should be monitored weekly until the abnormalities resolve, stabilize, or return to baseline levels.

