### 16.2 Appendix 2: Liver event and Laboratory trigger Definitions and Follow-up Requirements

**Table 16-2 Follow up requirements for liver events and laboratory triggers**

Criteria	Actions required	Follow-up monitoring
Potential Hy's Law case a	Discontinue the study treatment immediately Hospitalize, if clinically appropriate Establish causality Record the AE and contributing factors (e.g., conmeds, med hx, lab) in the appropriate CRF	ALT, AST, TBL, Alb, PT/INR, ALP and GGT until resolution c (frequency at investigator discretion)
ALT or AST		
> 8 × ULN	Discontinue the study treatment immediately Hospitalize if clinically appropriate Establish causality Record the AE and contributing factors (e.g., conmeds, med hx, lab) in the appropriate CRF	ALT, AST, TBL, Alb, PT/INR, ALP and GGT until resolution c (frequency at investigator discretion)
> 3 × ULN and INR > 1.5	Discontinue the study treatment immediately Hospitalize, if clinically appropriate Establish causality Record the AE and contributing	ALT, AST, TBL, Alb, PT/INR, ALP and GGT until resolution c (frequency at investigator discretion)

Criteria	Actions required	Follow-up monitoring
	factors (e.g., conmeds, med hx, lab) in the appropriate CRF	
> 5 to $\leq$ 8 $\times$ ULN	
Repeat LFT within 48 hours
 
If elevation persists, continue follow-up monitoring
 
If elevation persists for more than 2 weeks, discontinue the study drug
 
Establish causality
 
Record the AE and contributing factors (e.g., conmeds, med hx, lab) in the appropriate CRF
	
ALT, AST, TBL, Alb, PT/INR, ALP and GGT until resolutionc (frequency at investigator discretion)

> 3 $\times$ ULN accompanied by symptoms b	
Discontinue the study treatment immediately
 
Hospitalize if clinically appropriate
 
Establish causality
 
Record the AE and contributing factors (e.g., conmeds, med hx, lab) in the appropriate CRF
	
ALT, AST, TBL, Alb, PT/INR, ALP and GGT until resolutionc (frequency at investigator discretion)

> 3 to $\leq$ 5 $\times$ ULN (subject is asymptomatic)	
Repeat LFT within the next week
 
If elevation is confirmed, initiate close observation of the subject
	
Investigator discretion
 
Monitor LFT within 1 to 4 weeks

ALP (isolated)		

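### Three liver stopping rules differ, none is given precedence, and the mandatory stopping list in Section 9.1.1 cites only one of the sections that hold them

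*Protocol*

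**What the plan says.** **Table 6-6 (Protocol 6.5.1.2).** The introduction reads "Recommended dose modifications for isolated ALT or AST elevation are listed in" this table, but the criteria in it name ALT only. For isolated ALT of 3 to 5×ULN the dose is kept. The stop rule begins "Discontinue subject from the study treatment if elevation ALT" and sets a level of at least 3×ULN for a normal baseline. For a raised baseline the level is the lower of 3×baseline and 5×ULN. It also needs one added feature: symptoms or decompensation, rising tests, or at least four weeks' persistence. A separate row orders a permanent stop when ALT is at that level "combined with increased direct bilirubin OR For subjects with elevated baseline ALT" (the second half of the quote opens the raised-baseline version of the same row).

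**Section 6.5.2.1.** Treatment stops at once for AST or ALT above 3×ULN with total bilirubin above 2×ULN, unless cholestasis explains it. With a raised baseline, multiples of baseline are added.

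**Table 16-2 (Appendix 2).** This has its own column of required actions. It orders immediate stops for, among others, a potential Hy's Law case, ALT or AST above 8×ULN, and above 3×ULN with INR above 1.5.

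**Routing.** Section 6.5.1 sends mandatory permanent discontinuation to Sections 9.1.1 and 6.2.2. For liver chemistry, 9.1.1 cites only 6.5.1.2. Section 6.1.4 cites 6.5.2 in general terms. Table 16-2 appears in the table list, the Amendment 2 log and the appendix itself, but no operative section refers to it. Section 8.5.1.1 points DILI to 6.5.1.2, although the DILI criteria are in 6.5.2.1.

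**The concern.** The protocol warns, in Section 6.5.1.2, that this drug can cause fatal liver injury. An investigator who starts from the mandatory list in 9.1.1 is led to Table 6-6. For some results Table 6-6 orders no stop, or tells the site to keep the dose, while another section orders an immediate stop. The nearest thing to a ranking, the note that modifications follow the worst preceding toxicity, concerns the toxicity and not which table prevails. In a multi-center study the same laboratory result could therefore be handled differently from site to site.

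**Working it through.** The plan states no figure to reproduce here. The check sets the rules side by side and applies them to the same results. All values are multiples of ULN; b is a raised baseline ALT. Entry allows ALT below 3 (Section 5.2, criterion 3), so b between 1 and 3 can occur.

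**Step 1. The combined ALT and bilirubin stop**

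| | Table 6-6 | 6.5.2.1 | Table 16-2 (potential Hy's Law) |
|---|---|---|---|
| Enzyme | ALT | AST or ALT | ALT or AST |
| Bilirubin | direct, increased | total >2; also >2×baseline if a baseline value is raised | total >2 |
| ALT level, normal baseline | ≥3 | >3 | >3 |
| ALT level, baseline b | min(3b, 5) | min(max(2b, 3), 5) | 3 |
| Cholestasis exception | none | ALP >2 with R <2 | ALP >2 |

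**Step 2. ALT threshold by baseline**

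| b | Table 6-6 | 6.5.2.1 | Table 16-2 |
|---|---|---|---|
| 1.5 | min(4.5, 5) = 4.5 | min(max(3, 3), 5) = 3 | 3 |
| 2.0 | min(6, 5) = 5 | min(max(4, 3), 5) = 4 | 3 |
| 2.5 | min(7.5, 5) = 5 | min(max(5, 3), 5) = 5 | 3 |

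The largest gap among these is 5 − 3 = 2×ULN.

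**Step 3. Decisions on the same result**

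| Result | Table 6-6 | 6.5.2.1 | Table 16-2 |
|---|---|---|---|
| A. Baseline ALT 2, baseline total bilirubin normal; now ALT 3.5, total bilirubin 2.5, ALP not raised | no stop (3.5 < 5) | no stop (3.5 not > 4) | stop |
| B. Normal baseline, asymptomatic; ALT 3.5, total bilirubin 1.4, direct bilirubin raised | permanent stop | no stop (1.4 not > 2) | no stop |
| C. Normal baseline, asymptomatic, no earlier abnormal test; ALT 4, INR 1.6 | keep dose | no stop | stop |
| D. Normal baseline, asymptomatic, no earlier abnormal test; ALT 9 | no stop yet | no stop | stop |
| E. AST 9, ALT 2 | no stop (ALT only) | no stop | stop |
| F. Normal baseline; ALT 4, total bilirubin 2.5, direct raised, ALP normal | stop | stop | stop |

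The profiles were chosen to probe the boundaries and say nothing about frequency. C assumes that the site does not read INR 1.6 as hepatic decompensation; if it does, Table 6-6 also stops. E takes the table's criteria literally; the introductory sentence names AST, so a site could apply them to AST. Even then, a first asymptomatic AST of 9 would have none of the added features that Table 6-6 needs.

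B shows that Table 6-6 can be the strictest, while A, C and D show the reverse. Following one table alone does not settle the matter.

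**The case against.** The best reply is that the rules add up rather than conflict. Table 16-2 is current protocol text with required actions, Section 13.2 commits investigators to every instruction in the protocol, and updating the liver triggers was a stated purpose of Amendment 2. Section 6.5.2.1 orders its own stop. Section 9.1.1 obliges the investigator to stop when continuing would harm the subject, and also lists preventing laboratory abnormalities and unacceptable adverse events. On a stop-if-any reading, every listed stop applies.

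Much of this stands: nothing forbids a stop. A reader might infer that sites have no written stop above 8×ULN. The documents do not support that, because Table 16-2 supplies one. What remains is that the protocol nowhere states the stop-if-any reading, and that the mandatory list leads to a table that keeps the dose in case C.

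Two further contradictions are tempting but not firm:

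- **Asymptomatic ALT above 3 to 5×ULN.** Table 16-2 says "If elevation is confirmed, initiate close observation of the subject" and "Monitor LFT within 1 to 4 weeks", while Section 6.5.1.2 says "If the abnormalities are confirmed, serum liver tests should be monitored weekly until the abnormalities resolve" and Table 6-6 stops at four weeks. Observation does not prohibit a stop, and weekly testing fits within one to four weeks, so both can be followed.
- **ALT above 5 to 8×ULN.** Table 16-2 says "If elevation persists for more than 2 weeks, discontinue the study drug", against four weeks in Table 6-6. The Table 6-6 stop cell has no row label in the text as extracted, and any gap in days depends on an assumed testing grid.

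The footnote to Table 6-6, "total bilirubin (fractionated [direct and indirect], if total bilirubin" exceeds 2×ULN, might suggest that direct bilirubin would be missed below that level. Table 8-4 lists direct bilirubin in the chemistry panel, so this adds little. The wrong DILI reference in 8.5.1.1 has limited effect, since 6.5.2.1 itself asks for the PK sample.

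**Conclusion.** The concern holds as a misalignment without a stated hierarchy, together with an incomplete citation in the mandatory list. The firm differences are direct versus total bilirubin, a combined-stop ALT threshold of 5, 4 or 3×ULN at baseline ALT 2×ULN, and immediate stops for ALT or AST above 8×ULN and for above 3×ULN with INR above 1.5 that appear only in Table 16-2. The rules agree on the classic picture in case F. The documents give no liver-event rate, so the number of subjects affected cannot be estimated.

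This should be fixed because following 9.1.1 and Table 6-6 as written can keep a subject on treatment when another section orders a stop. It is a matter of safety conduct and leaves the primary analysis method untouched. A reader might infer that each earlier liver stop costs a responder. The documents do not support that: under Section 9.1.1, stopping treatment is not by itself withdrawal from the study, and Section 12.4.3 counts as non-responders those who discontinue from the trial before Week 26.

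**What to change.** Amend the protocol in four places:

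1. In 9.1.1 and 6.5.1.2, cite 6.5.2.1 and Table 16-2 as liver stopping criteria.
2. State that treatment stops if any one of the three rules requires it.
3. State that Table 6-6 applies to AST as well as ALT.
4. In 8.5.1.1, change the DILI reference to 6.5.2.1.

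The sponsor should accept one consequence knowingly. Under stop-if-any, the unadjusted threshold of 3×ULN in Table 16-2 governs whenever total bilirubin is above 2×ULN and ALP is not above 2×ULN, so the baseline adjustments elsewhere lose their effect for those subjects.

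No visits or tests are added. The change needs approval by the sponsor and the IRB/IEC, and by health authorities where required (Section 14.1). A few subjects may stop treatment earlier, in a population with no established alternative beyond supportive care (Section 1.1). Only those who also leave the trial before Week 26 become non-responders by rule, at 1/20 = 5 percentage points each if they would otherwise have responded. For example, 8/20 (exact 90% CI 21.7–60.6%, as in Table 12-2) would become 7/20 (17.7–55.8%).

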### **6.5.2 Follow-up for toxicities**

Subjects whose treatment is interrupted or permanently discontinued due to an adverse event or clinically significant laboratory value, must be followed up at least once a week (or more frequently if required by institutional practices, or if clinically indicated) for 4 weeks, and subsequently at approximately 4-week intervals, until resolution or stabilization of the event, whichever comes first. Appropriate clinical experts such as ophthalmologist, endocrinologist, dermatologist, psychiatrists etc. should be consulted as deemed necessary.

All subjects must be followed up for adverse events and serious adverse events for 30 days following the last doses of eltrombopag.

#### **6.5.2.1 Follow up on potential drug-induced liver injury (DILI) cases**

Subjects with transaminase increase combined with TBIL increase may be indicative of potential severe drug-induced liver injury (DILI), and should be considered as clinically important events.

The threshold for further work-up for potential severe DILI may depend on the subject's baseline AST/ALT and TBIL value; subjects meeting any of the following criteria will require further follow-up as outlined below:

- For subjects with normal ALT and AST and TBIL value at baseline: AST or ALT  $> 3.0 \times$  ULN combined with TBIL  $> 2.0 \times$  ULN
- For subjects with elevated AST or ALT or TBIL value at baseline: [AST or ALT  $> 2 \times$  baseline AND  $> 3.0 \times$  ULN] OR [AST or ALT  $> 5.0 \times$  ULN], combined with [TBIL  $> 2 \times$  baseline AND  $> 2.0 \times$  ULN]

Medical review needs to ensure that liver test elevations are not caused by cholestasis, defined as ALP elevation  $> 2.0 \times$  ULN with R value  $< 2$ .

Note: (The R value is calculated by dividing the ALT by the ALP, using multiples of the ULN for both values. It denotes whether the relative pattern of ALT and/or ALP elevation is due to cholestatic (R  $\leq 2$ ), hepatocellular (R  $\geq 5$ ), or mixed (R  $> 2$  and  $< 5$ ) liver injury).

In the absence of cholestasis, these subjects should be immediately discontinued from study treatment, and repeat liver function test (LFT) testing as soon as possible, preferably within 48 hours from the awareness of the abnormal results. The evaluation should include laboratory tests, detailed history, physical assessment, obstructions/compressions, etc.

1. Laboratory tests should include ALT, AST, albumin, creatine kinase, total bilirubin, direct and indirect bilirubin, GGT, prothrombin time (PT)/ International Normalized Ratio (INR) and alkaline phosphatase.
2. A detailed history, including relevant information, such as review of ethanol, concomitant medications, herbal remedies, supplement consumption, history of any pre-existing liver conditions or risk factors, should be collected.
3. Further testing for acute hepatitis A, B, C or E infection and liver imaging (e.g. biliary tract) may be warranted.
4. Obtain PK sample, as close as possible to last dose of eltrombopag.
5. Additional testing for other hepatotropic viral infection (cytomegalovirus (CMV), Epstein-Barr virus (EBV) or herpes simplex virus (HSV)), autoimmune hepatitis or liver biopsy may be considered as clinically indicated or after consultation with specialist/hepatologist.

All cases confirmed on repeat testing meeting the laboratory criteria defined above, with no other alternative cause for LFT abnormalities identified should be considered as "medically significant", thus, met the definition of SAE and reported as SAE using the term "potential drug-induced liver injury". All events should be followed up with the outcome clearly documented.

## **6.6 Additional treatment guidance**

### **6.6.1 Treatment compliance**

The investigator must promote compliance by instructing the subject to take the study treatment exactly as prescribed and by stating that compliance is necessary for the subject's safety and the validity of the study. The subject must also be instructed to contact the investigator if he/she is unable for any reason to take the study treatment as prescribed. Compliance will be assessed by the investigator and/or study personnel at each visit using pill

counts and information provided by the subject. This information should be captured in the source document at each visit. All study treatment dispensed and returned must be recorded in the Drug Accountability Log.

### **6.6.2 Emergency breaking of assigned treatment code**

This study is an open-label, single arm study.

## **6.7 Preparation and dispensation**

Each study site will be supplied with study drug in packaging as described under investigational and control drugs section.

A unique medication number is printed on the study medication label.

As per the treatment assigned to the subject, investigator staff will select the study treatment to dispense to the subject.

### **6.7.1 Handling of study treatment and additional treatment**

#### **6.7.1.1 Handling of study treatment**

Study treatment must be received by a designated person at the study site, handled and stored safely and properly and kept in a secured location to which only the investigator and designated site personnel have access. Upon receipt, all study treatment must be stored according to the instructions specified on the labels and in the [Investigator's Brochure]. Clinical supplies are to be dispensed only in accordance with the protocol. Technical complaints are to be reported to the respective Novartis Country Organization (CO) Quality Assurance.

Medication labels will be in the local language and comply with the legal requirements of each country. They will include storage conditions for the study treatment but no information about the subject except for the medication number.

The investigator must maintain an accurate record of the shipment and dispensing of study treatment in a drug accountability log. Monitoring of drug accountability will be performed by monitors during site visits or remotely and at the completion of the trial. Subjects will be asked to return all unused study treatment and packaging at the end of the study or at the time of discontinuation of study treatment.

At the conclusion of the study, and as appropriate during the course of the study, the investigator will return all unused study treatment, packaging, drug labels, and a copy of the completed drug accountability log to the Novartis monitor or to the Novartis address provided in the investigator folder at each site.

#### **6.7.1.2 Handling of additional treatment**

Not applicable. There is no specific handling and storage requirements for non-study treatment in this study.

